## 7.8. 12-Lead Standard Electrocardiogram

All 12-lead standard ECG measurement results, overall interpretation, and findings will be listed in [Listing 20](#), [Listing 21](#), and [Listing 22](#).

12-lead standard ECG results will be summarized in tables and figures:

- Tabularly, 12-lead standard ECG change in overall interpretation from baseline will be shown by Dose Group and time point ([Table 29](#)).
- Tabularly, by parameter, Dose Group, time point, and toxicity grade (including maximum severity post-baseline) ([Table 30](#)).
- Tabularly, by summary statistics for change from baseline, reported by parameter, Dose Group, and time point ([Table 31](#)).
- Tabularly, by Dose Group, time point, and sex based on QTcF categories according to the ICH Guideline E14 “Clinical Evaluation of QT/QTc Interval Prolongation and Proarrhythmic Potential for Non-Antiarrhythmic Drugs” (protocol v6.0 Section 10.5.2). ([Table 32](#)).
- Graphically, using box plots of change from baseline by parameter, Dose Group, and time point ([Figure 54](#), [Figure 55](#), [Figure 56](#), [Figure 57](#), [Figure 58](#), [Figure 59](#)).

The following parameters will be presented (in order): PR interval, QRS duration, QT interval, QTcF interval, RR interval, and mean ventricular rate.

Unscheduled 12-lead standard ECG measurements will be listed but excluded from tabular and graphical summaries. Individual interval measurements will be presented in listings along with overall interpretation

and comments. Other ECG findings besides interpretation will also be included in listings. Repeated ECG due to clinic error or technical problem will be used for all analyses instead of the original ECG result. Additional ECG measurements taken as follow-up for safety will be included in listings and in computing maximum severity post baseline, but not as separate time points in summary tables. For repeats that were done due to delayed dosing, the median of the last triplicate ECG measurement prior to dosing will be considered as baseline for that subject.

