7.1.6 Electrocardiograms

Standard 12-lead ECGs to assess heart rate, rhythm, and PR, QRS, QT, and QTc interval durations will be obtained at times specified in [Appendix A](#).

ECGs (triplicate readings, at least 1 minute apart within a 15-minute period), will be taken after at least 5 minutes in the supine position. The pre-dose ECGs on days of dosing will be taken within 60 minutes of study drug dosing. Post dose ECGs on days of dosing will be taken at 4 hours (\pm 10 minutes) after SC dosing. Post dose ECGs on days of dosing will be taken at 1 hour (\pm 10 minutes) from start of infusion for IV administration in Part 3.

ECGs will also be taken at the following timepoints:

- Day 7, Day 30, and Unscheduled visits for SAD
- Day 21, Day 30, Day 45, and Unscheduled visits for MAD
- Day 52 and Unscheduled visits for BA

The screening ECG will be used by the PI to determine a subject's eligibility for enrolment. The Day 1 pre-dose ECG will be reviewed to determine if subjects can be dosed.

All ECGs will be reviewed by the PI or designee. ECGs with the following readings will be considered acceptable for trial participation and will not be considered abnormal for trial purposes unless the PI or physician designee believes they represent a new medical condition when compared to baseline ECGs. In such cases an AE will be documented, and the subject will be followed for safety evaluations as appropriate. The following pre-existing conditions identified at enrolment will not be considered AEs:

- Sinus bradycardia,
- Sinus arrhythmia,
- Subjects without a history of prolonged QTc and an abnormal QTc interval at Screening will undergo repeat ECG assessment within the screening period before randomization to confirm prolongation. If the repeat ECG QTcF is within normal limits (see [Appendix B](#)) the subject may be considered for enrolment.

The Sponsor may review all or individual screening ECGs or may delegate to determine if meets intention of entry criteria goal of enrolling healthy normal subjects.

If a subject has possible cardiac-related symptoms, repeat ECGs will be obtained every 30 minutes (± 3 minutes) until the waveform reverts to its baseline appearance, or symptoms resolve, or are determined not to be cardiac-related. Subjects with cardiac-related symptoms that are associated with ECG changes will be transferred to appropriate emergency department for further evaluation and treatment at the discretion of the PI.

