10.5.2 Clinical Safety Labs, Vital Signs, and Electrocardiograms

Baseline for clinical safety labs, vital signs, and ECGs will be defined as the last result obtained before the dose of study product. For crossover data, there will be a separate baseline for each treatment. Changes from baseline for clinical safety labs, vital signs, and ECGs results will be summarized by dose group and time point. Clinical safety labs and vital signs will be graded ([Appendix B](#)) and summarized by severity, group, and visit. Rules for analyzing replicates for a safety time point (labs, vital signs, ECG), if obtained, will be described in the SAP.

Treatment-emergent abnormal laboratory test results will be identified. Treatment-emergent abnormal laboratory tests are tests for which the result was not graded as mild or worse at baseline but graded as mild or worse after dosing. Laboratory tests graded as mild at baseline, but moderate or worse any time after dosing will also be regarded as treatment-emergent abnormal laboratory test results.

ECG measurements will include heart rate, RR interval, QT interval, QTcF interval, PR interval, and QRS duration. Baseline for ECG measurements is defined per protocol as the value pre-dosing on Day 1 (or pre-dosing on Day 21 for period 2 of Part 3). Change from baseline will be summarized descriptively by regimen at each scheduled evaluation. QTc results will be summarized categorically according to the ICH Guideline E14 “Clinical Evaluation of QT/QTc Interval Prolongation and Proarrhythmic Potential for Non-Antiarrhythmic Drugs” (October 2005):

- QTcF >450 ms, males only
- QTcF >470 ms, females only
- QTcF >480 ms
- QTcF >500 ms
- QTcF increases from baseline by at least 30 ms but less than 60 ms
- QTcF increases from baseline by at least 60 ms

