**Table 30: ECG Toxicity Grade by Parameter, Severity, Dose Group, and Time Point**

[Implementation Note: If there is not at least 1 Mild, Moderate, or Severe Event for Max Severity Post-Baseline, then only the Max Severity Post-Baseline row will be shown for the parameter.]

Dose Group	Time Point	N	Mild n (%)	Moderate n (%)	Severe n (%)
PR Interval					
SAD Any Dose	Baseline	x	x (x)	x (x)	x (x)
	Max Severity Post Baseline				
	Day 1, 4 h Post-Dose	x	x (x)	x (x)	x (x)
	Day 7	x	x (x)	x (x)	x (x)
	Final Visit	x	x (x)	x (x)	x (x)
SAD 1 mg	Baseline	x	x (x)	x (x)	x (x)
	...	x	x (x)	x (x)	x (x)
SAD 10 mg	Baseline	x	x (x)	x (x)	x (x)
	...	x	x (x)	x (x)	x (x)
Placebo	Baseline	x	x (x)	x (x)	x (x)
	...	x	x (x)	x (x)	x (x)
QTcF Interval					
SAD Any Dose	Baseline	x	x (x)	x (x)	x (x)
	...	x	x (x)	x (x)	x (x)
Notes: The “Max Severity Post Baseline” rows indicate the maximum severity of ECG Results Related to study treatment experienced by each subject at any time point post baseline, including unscheduled assessments.					
N = Number of subjects in Safety Population with the ECG results assessed at the respective time point.					

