**Table 32: Summary of QTcF by Dose Group and Time Point**

[Implementation Note: For all QTcF categories that specified gender, N based on gender should be used for calculating proportions]

QTcF Category	Time Point	SAD Any Dose	SAD 1 mg	SAD 10 mg	Placebo
		n / N (%)	n / N (%)	n / N (%)	n / N (%)
QTcF >450 ms, Male	Day 1, 4 h Post-Dose	x / x (x)	x / x (x)	x / x (x)	x / x (x)
	Day 7	x / x (x)	x / x (x)	x / x (x)	x / x (x)
	Final Visit	x / x (x)	x / x (x)	x / x (x)	x / x (x)
QTcF >470 ms, Female	Day 1, 4 h Post-Dose	x / x (x)	x / x (x)	x / x (x)	x / x (x)
	...	x / x (x)	x / x (x)	x / x (x)	x / x (x)
QTcF >480 ms	Day 1, 4 h Post-Dose	x / x (x)	x / x (x)	x / x (x)	x / x (x)
	...	x / x (x)	x / x (x)	x / x (x)	x / x (x)
QTcF >500 ms	Day 1, 4 h Post-Dose	x / x (x)	x / x (x)	x / x (x)	x / x (x)
	...	x / x (x)	x / x (x)	x / x (x)	x / x (x)
30 ms ≤ QTcF increases from baseline < 60 ms	Day 1, 4 h Post-Dose	x / x (x)	x / x (x)	x / x (x)	x / x (x)
	...	x / x (x)	x / x (x)	x / x (x)	x / x (x)
QTcF increases from baseline ≥ 60 ms	Day 1, 4 h Post-Dose	x / x (x)	x / x (x)	x / x (x)	x / x (x)
	...	x / x (x)	x / x (x)	x / x (x)	x / x (x)

N= Number of subjects in Safety Population with the ECG results assessed at the respective time point. N is calculated based on specified sex for "QTcF >450 ms, Male" and "QTcF >470 ms, Female" categories.

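### Table 32 counts QTcF outliers at three scheduled times only, so one seen only on an unscheduled ECG enters none of its categories and reaches Table 30 only under conflicting wording

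*SAP*

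**What the plan says.** Protocol 10.5.2 plans the outlier summary: "QTc results will be summarized categorically according to the ICH Guideline E14". It lists six QTcF categories: above 450 ms (males), above 470 ms (females), above 480 ms, above 500 ms, a rise of 30 to under 60 ms, and a rise of at least 60 ms.

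The SAP implements this in Table 32, titled "Summary of QTcF by Dose Group and Time Point". Each category has rows for Day 1 4 h, Day 7 and the final visit. The denominator is tied to the visit: "N= Number of subjects in Safety Population with the ECG results assessed at the respective time point".

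SAP 7.8 sets the rule for other ECGs: "Unscheduled 12-lead standard ECG measurements will be listed but excluded from tabular and graphical summaries". Later in the same paragraph it says: "Additional ECG measurements taken as follow-up for safety will be included in listings and in computing maximum severity post baseline". That sentence goes on to say that these ECGs do not form separate time points in the summary tables.

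Table 30 grades PR and QTcF by toxicity. Its footnote describes the maximum row as the "maximum severity of ECG Results Related to study treatment experienced by each subject at any time point post baseline, including unscheduled assessments".

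Protocol 7.1.6 makes off-schedule ECGs a planned part of the trial: "If a subject has possible cardiac-related symptoms, repeat ECGs will be obtained every 30 minutes". It also names unscheduled visits as ECG occasions in the single-dose part.

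**The concern.** ECGs belong to the primary safety assessment (Protocol 3.3.1), and Table 32 is the only display that counts subjects in the protocol's QTcF categories. An ECG prompted by cardiac symptoms is a natural place to look for a marked prolongation, yet the layout of Table 32 gives it nowhere to go.

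A reader who takes the count of QTcF above 500 ms from Table 32 would be reading a count for three scheduled visits, possibly without realising it. In groups this small, one subject changes the result visibly.

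**Working it through.** No alpha, power or sample-size figure bears on this point. The check is a reading of the rules plus simple counts.

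**Scheduled ECGs against Table 32.** After dosing, Part 1 schedules ECGs at 4 h on Day 1, on Day 7 and on Day 30 (Protocol 7.1.6 and Table 11). That makes 3 times, and Table 32 has the same 3. The intervals with no scheduled ECG are:
- 4 h to Day 7 (taken as 144 h): 144 − 4 = about 140 h.
- Day 7 to Day 30: 30 − 7 = 23 days.

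**An illustrative subject.** Assume a baseline of 445 ms, 430 ms at 4 h, 505 ms on a symptom-driven ECG on Day 3, 425 ms on Day 7, and nothing notable at the final visit.
- Changes from baseline: 430 − 445 = −15 ms; 505 − 445 = +60 ms; 425 − 445 = −20 ms.
- Table 32 as planned: no contribution to any category.
- All post-dose ECGs: the subject is above 480 ms, above 500 ms, above the sex-specific limit, and has a rise of at least 60 ms. The last item needs a baseline of 505 − 60 = 445 ms or lower.

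The result does not depend on whether the Day 3 tracing is called unscheduled or follow-up for safety. Under the first label SAP 7.8 excludes it from tables. Under the second it is not a separate time point, and Table 32 has only time-point rows.

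**Size at planned numbers (Protocol Table 1).** Rezafungin: 3 at 1 mg, 6 at 10 mg, 3 + 6 = 9 overall. Pooled placebo: 1 + 2 = 3. The intervals are Wilson 95%, the SAP's method for percentages; Table 32 itself shows none. With z = 1.96 and p = x/n, the limits are [p + z²/(2n) ± z√(p(1−p)/n + z²/(4n²))] / (1 + z²/n).

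| Group | Counted in Table 32 | Counted with an any-time row |
|---|---|---|
| 10 mg | 0/6 (0%) | 1/6 = 17% (3.0 to 56.4) |
| 1 mg, or pooled placebo | 0/3 (0%) | 1/3 = 33% (6.1 to 79.2) |
| Any dose | 0/9 (0%) | 1/9 = 11% (2.0 to 43.5) |

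Each row assumes one such subject in that group and no other outlier.

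**Ever in a category.** Even scheduled ECGs alone do not give this count. One subject at each of the three times could be 1, 2 or 3 different people, because the rows overlap and no row combines them.

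**Does Table 30 fill the gap?** In part.
1. The exclusion sentence in SAP 7.8 has no exception. The parallel laboratory and vital-sign sentences (SAP 7.6 and 7.7) exempt the derivation of maximum post-baseline severity. The follow-up sentence and the Table 30 footnote point the same way, and SAP 5.1 defines a denominator for an ECG maximum row. A programmer working from the exclusion sentence could still leave these ECGs out of Table 30. The SAP does not define where unscheduled ends and follow-up for safety begins.
2. The footnote confines the maximum row to treatment-related results, so an outlier judged unrelated could drop out.
3. In Appendix B, Grade 3 is a QTc of at least 500 ms or a rise of at least 60 ms; Grade 2 is 480 to 499 ms or a rise of 30 to 59 ms. Neither is sex-specific. The six protocol categories cannot be recovered from these merged grades.

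**The case against.** The strongest reply is that the report does carry the event. Listing 20 gives every ECG, scheduled or not, with its grade and change from baseline. Under its footnote, Table 30 would show the 505 ms reading as Severe. An ECG judged to be a new condition is also recorded as an adverse event. With 12 subjects planned in the two cohorts analysed, a reader could work out the ever-counts from Listing 20. All of this stands. A reader might infer from Table 32 and the exclusion sentence that such ECGs are reported as zero throughout, or can never be counted; the documents do not support that.

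A second reply is that the SAP does not depart from the protocol. That is also right. Protocol 10.5.2 does not ask for an any-time count, and its preceding sentence speaks of change from baseline at scheduled evaluations. The case for the extra row is completeness of the safety display, not a breach of the protocol.

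A third is that oversight during the trial did not rest on Table 32. The cohort halting rule on QTcF (Protocol 8.7.2) is not limited to scheduled times and works through a separate halting report (Protocol 3.1.3). It would be wrong to infer that Table 32 could hide a halting event from the safety committee.

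What the replies leave untouched is the table itself and the conflict in the wording. A listing is not a count, and Table 30 cannot supply the protocol's categories.

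**Conclusion.** The point holds for Table 32. A QTcF outlier seen only on an unscheduled or symptom-driven ECG is counted in none of its six categories, and the number of subjects ever in a category cannot be read from it. The event would appear in Listing 20 and, depending on which of the conflicting passages is followed, as a merged Grade 3 in the Table 30 maximum row.

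One missed subject is 17 percentage points at 10 mg and 33 at 1 mg or in pooled placebo. These figures assume planned group sizes, since the documents do not give the numbers actually enrolled.

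The documents do not say that any such ECG occurred. The SAP attributes the early termination to safety concerns without naming them, so no link to QTcF should be inferred. The matter is one of display and consistency, worth correcting because the correction is cheap.

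**What to change.** 1. **Table 32.** Add to each category a row for any post-dose ECG, including unscheduled ones. Count each subject once, on the worst post-dose QTcF or, for the change categories, the largest increase from baseline. Set N to subjects with any post-dose ECG, by sex for the two sex-specific categories. Handle triplicates as in the scheduled rows.
2. **SAP 7.8.** Attach an exception to the unscheduled-ECG sentence for maximum severity post-baseline, matching 7.6 and 7.7, and for the new Table 32 row.
3. **Table 30 footnote.** Delete the restriction to treatment-related results, so that it agrees with 7.8.

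The cost is six table rows, one amended sentence and one deleted phrase, with no new data. There is a small downside: subjects with symptom-driven ECGs contribute more readings to the any-time row and so have more chances to cross a threshold. A short footnote stating that the row includes unscheduled ECGs would cover this.

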## 7.9. Concomitant Medications

All medications will be coded using the current version of the WHO Drug dictionary. The use of prior and concomitant medications taken during the study will be summarized by ATC 1 and ATC 2 (separately in [Table 33](#) for prior medications and [Table 34](#) for concomitant medications). Individual subject listings will be presented for all prior and concomitant medications (separately in [Listing 23](#) for prior medications and [Listing 24](#) for concomitant medications).

## 8. PHARMACOKINETICS

Time points below the lower limit of quantification (LLOQ), referred to as below limit of quantification (BQL), preceding the first PK concentration above the LLOQ will be imputed as 0 for plotting and for all calculations including NCA and summary statistics. All other BQL values will be missing for analysis purposes. There will be no imputation of missing concentrations. A geometric mean (GM) of concentrations will be treated as missing for sets of data points containing more than 1 BQL value.

Collection of plasma samples outside of the protocol defined time window for the time point will not result in exclusion of the sample result from noncompartmental analysis (NCA). Plasma samples collected out of window will be evaluated on a case-by-case basis. Samples will be considered substantially out of window if PK samples were not collected within  $\pm$  10 min for the 0.5 hour time point,  $\pm$  20 min of the targeted collection time (nominal time point) for time points 12 hours post-dose and earlier and within  $\pm$  1 hour for nominal time points from 24 to 144 hours post-dose, and  $\pm$  2 days on Day 14 and Day 30. Results from substantially out of window samples will be excluded from concentration summary statistics by nominal time points and plots of mean concentration, but included in NCA and in plots of individual concentrations.

Drug concentrations in plasma will be listed for subjects in Cohort 2, including placebo, with BQL and PK analyses-excluded samples indicated and with separate columns for concentrations reported by the lab and concentrations used for analysis ([Listing 31](#)). The column containing concentrations reported from the lab may include codes such as “BQL” or “QNS” (Quantity Not Sufficient) while the column containing concentrations used for analysis will contain numeric data only, including imputed values such as zeros for pre-dose timepoints reported as BQL. The listings will also indicate the nominal time (i.e., the planned time) and actual post-dose time in h associated with the sample.

The PK Analysis Subset will be used when summarizing PK concentrations. Summary statistics will be given for rezafungin concentrations by nominal time ([Table 35](#)).

Rezafungin concentrations will be also be shown graphically:

- Individual subject concentration-time profiles within 144 hours post-dose (Day 7) with y-axis on the linear scale ([Figure 60](#)).
- Individual subject concentration-time profiles within 144 hours post-dose (Day 7) with y-axis on the logarithmic scale ([Figure 61](#)).
- Individual subject concentration-time profiles for all time points with y-axis on the linear scale ([Figure 62](#)).
- Individual subject concentration-time profiles for all time points with y-axis on the logarithmic scale ([Figure 63](#)).
- GM concentration-time profiles within 144 hours post-dose (Day 7) y-axis on the linear scale. Error bars will show the mean  $\pm$  1 SD ([Figure 64](#)).
- GM concentration-time profiles within 144 hours post-dose (Day 7) y-axis on the logarithmic scale ([Figure 65](#)).
- GM concentration-time profiles for all time points with y-axis on the linear scale. Error bars will show the mean  $\pm$  1 SD ([Figure 66](#)).
- GM concentration-time profiles for all time points with y-axis on the logarithmic scale ([Figure 67](#)).

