## 5. GENERAL STATISTICAL CONSIDERATIONS

### 5.1. General Principles

Safety and PK data will be summarized by Dose Group, following the order shown in Section 3.3. Summary statistics for continuous data will include the mean, standard deviation (SD), median, minimum value (min), and maximum value (max). Summary statistics for discrete data will include counts and percent and may include confidence intervals (CIs) for the percent. When 95% CIs are given for a percent, Wilson Score CIs will be used. All subjects that are randomized will be included in the summaries of demographics, the Safety Population will be used for summaries of safety endpoints, and PK Population or PK Analysis Subset will be used for summaries of PK endpoints.

Generally, for summaries of safety endpoints, denominators will use the number of subjects in the Safety Population. Denominators for study time points of solicited local reactogenicity symptoms, clinical laboratory results, VS, and ECG results will use the number of subjects with an observed result at the time point for the parameter or symptom. Denominators for the conceptual “Max Severity Post-Baseline” time point for solicited local reactogenicity symptoms, clinical laboratory results, VS, and ECG results will use the number of subjects with an observed result for the parameter obtained post-dose.

The sort order of the listings as is indicated in the Implementation Note for each listing shell (Appendix 3).

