## 8.1. Noncompartmental Analysis

PK parameters will be estimated through an NCA using Phoenix® WinNonlin® version 8.2 or later (Certara, Princeton, NJ). Actual post-dose time will be used for the estimation of PK parameters instead of nominal time. Individual PK parameter estimates will be listed. PK Analysis Subset will be used when summarizing PK parameters. Summary tables including mean, SD, min, max, median, coefficient of variation (CV %), and GM will be presented ([Table 36](#)). Definition of CV is provided below.

For an independent identically distributed random sample  $\{x_1, x_2, \dots, x_n\}$  from a log-normal distribution, let  $s^2$  be the sample variance statistic of the natural log-transformed values of the sample. The CV was defined as:

$$CV = \sqrt{\exp(s^2) - 1}$$

Phoenix® WinNonlin® NCA will use the following settings to compute parameters from plasma rezafungin concentration data:

- Linear Up Log Down calculation method
- Uniform weighting
- Extravascular Dosing
- Lambda Z Acceptance Criteria
  - Rsq\_adjusted  $\geq 0.90$
  - Span  $\geq 3.0$  half-lives
  - Includes at least 3 timepoints after  $T_{max}$

All estimable PK parameters and terminal phase PK parameters that meet Lambda Z acceptance criteria will be listed in [Listing 32](#). A definition for each PK parameter for the SAD cohorts are defined below.

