## 14.5 Pharmacokinetics

**Table 35: Rezafungin Concentrations in Plasma, SAD 10 mg Dose Group**

Subject ID	Nominal Time a (h)													
	0	0.5	1	2	4	6	8	12	24	48	96	144	312 (Day 14)	696 (Day 30)
PHU.00123	x	x	x	x	x	x	x	x	x	x	x	x	x	x
PHU.00124	x	x	x	x	x	x	x	x	x	x	x	x	x	x
PHU.00125	x	x	x	x	x	x	x	x	x	x	x	x	x	x
...	x	x	x	x	x	x	x	x	x	x	x	x	x	x
Statistics														
Nb	x	x	x	x	x	x	x	x	x	x	x	x	x	x
Mean	x	x	x	x	x	x	x	x	x	x	x	x	x	x
SD	x	x	x	x	x	x	x	x	x	x	x	x	x	x
GM	x	x	x	x	x	x	x	x	x	x	x	x	x	x
CV %	x	x	x	x	x	x	x	x	x	x	x	x	x	x
Min	x	x	x	x	x	x	x	x	x	x	x	x	x	x
Max	x	x	x	x	x	x	x	x	x	x	x	x	x	x

a Times are relative to time of dosing.

b Number of data points used to compute the summary statistics. For calculation of summary statistics, BQL values were imputed as 0 if they did not come after a PK sample concentration that is above the LLOQ and treated as missing otherwise.

Note: Samples that were collected substantially outside of the protocol-defined window are excluded from summary statistics (but not from NCA) and are indicated by an asterisks (\*).

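### A single zero-imputed BQL makes the concentration geometric mean 0, and Figures 64 and 66 put arithmetic mean ± SD bars on geometric-mean curves

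*SAP*

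**What the plan says.** SAP Section 8 gives three rules for BQL concentrations.

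- Values before a subject's first quantifiable sample "will be imputed as 0 for plotting and for all calculations including NCA and summary statistics".
- For the rest: "All other BQL values will be missing for analysis purposes".
- A safeguard for the GM: "A geometric mean (GM) of concentrations will be treated as missing for sets of data points containing more than 1 BQL value".

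Footnote b of Table 35 repeats the first two rules ("BQL values were imputed as 0 if they did not come after a PK sample concentration that is above the LLOQ") and adds nothing for a set with one zero. That table reports N, mean, SD, GM, CV%, minimum and maximum at each nominal time. The only definition of CV in the SAP is in Section 8.1, where s² is said to "be the sample variance statistic of the natural log-transformed values of the sample".

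For the figures, Section 8 specifies for Figure 66 "GM concentration-time profiles for all time points with y-axis on the linear scale. Error bars will show the mean" ± 1 SD, and words Figure 64 the same way for the first 144 hours. Figure 67 is described as "GM concentration-time profiles for all time points with y-axis on the logarithmic scale", and Figure 65 is its 144-hour counterpart. The shell titles of all four figures say Mean, not GM.

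**The concern.** The safeguard starts one value too late. A GM is a product, so one zero is enough to make it zero, and the SAP itself creates that zero by imputation. The result runs backwards: two BQL values give a blank cell, while one gives a printed GM of 0. A log-scale CV has no value for such a set, and a zero cannot be placed on the log axes of Figures 65 and 67.

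The second defect does not depend on BQL values. In Figures 64 and 66 the curve is geometric and the bars are arithmetic, so a reader cannot take the bars as spread around the plotted point.

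The plasma PK profile is a primary objective. After early termination the 10 mg group is the only source of PK data, with six active subjects planned. In so small a set one value can decide a displayed point.

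**Working it through.** The documents give no figure to reproduce here, no LLOQ and no concentrations. The rules come from SAP Sections 8 and 8.1; n = 6 is the planned active number in Cohort 2 (Protocol Table 1). All concentrations, BQL probabilities and CVs below are assumed.

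**One leading BQL.** Take 0, 10, 12, 15, 18, 20, where the 0 is an imputed BQL.

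- BQL count is 1, so the safeguard is not triggered.
- GM = (0 × 10 × 12 × 15 × 18 × 20)^(1/6) = 0.
- Arithmetic mean = 75/6 = 12.5; median = (12 + 15)/2 = 13.5.
- Sum of squared deviations = 1193 − 6 × 12.5² = 255.5; SD = √(255.5/5) = 7.15. Mean ± SD runs from 5.35 to 19.65, so the plotted GM of 0 falls below its own bar.
- CV = √(exp(s²) − 1) is undefined, because ln 0 is.
- If software silently drops ln 0, it reports (10 × 12 × 15 × 18 × 20)^(1/5) = 648,000^(1/5) = 14.5 on n = 5.
- If the 10 were also a leading BQL, the count would be 2 and the GM would be withheld.

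Pre-dose is not exposed as long as at least two active subjects contribute, since all should be BQL there. A BQL after the first quantifiable sample is set to missing and produces no zero. The exposed points are therefore mainly the early post-dose samples, which start at 0.5 h.

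**How often.** With independent chance p of a leading BQL per subject at a time point, P(exactly one of 6) = 6p(1 − p)⁵:

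- p = 5%: 0.30 × 0.774 = 23%
- p = 10%: 0.60 × 0.590 = 35%
- p = 17%: 1.02 × 0.394 = 40%

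**Bars against curve.** Under log-normality, mean/GM = √(1 + CV²), SD/GM = CV√(1 + CV²), and the geometric SD is exp(√ln(1 + CV²)). In units of the GM:

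| CV | Bar centre if arithmetic mean | Mean ± SD | GM ± SD | GM ×/÷ geometric SD |
|---|---|---|---|---|
| 30% | 1.044 | 0.731 to 1.357 | 0.687 to 1.313 | 0.746 to 1.341 |
| 50% | 1.118 | 0.559 to 1.677 | 0.441 to 1.559 | 0.624 to 1.604 |
| 100% | 1.414 | 0 to 2.828 | −0.414 to 2.414 | 0.435 to 2.299 |

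Bars read as arithmetic mean ± SD centre 4%, 12% and 41% above the curve. Read as GM ± SD, the lower limit is a negative concentration at CV 100%.

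**Late BQL values (minor).** Setting these to missing leaves the Table 35 arithmetic mean resting on the higher values. In 200,000 simulated sets of six log-normal values, with those below the LLOQ dropped and CV 30% to 50%, the mean is high by 4–13% when the true GM is 1.5 × LLOQ, 0.5–5% at 2 × LLOQ and under 1% at 3 × LLOQ.

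**The case against.** The strongest reply is that the arithmetic mean was intended in the figures. All four shell titles say Mean, and Section 8 elsewhere speaks of plots of mean concentration. On that reading the bars match the curve, a single zero still leaves a plottable mean, and the defect shrinks to a wrong word in Section 8 plus the GM and CV% rows of Table 35. This is possible, and the shell graphics are not available to settle it. But the text says GM for all four figures, so text and titles contradict each other under either reading.

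The first part is also conditional. It needs exactly one subject with a leading BQL at a post-dose time, and neither the LLOQ, the concentrations nor the number actually dosed in Cohort 2 is given. Software might drop ln 0 rather than return zero. That is true, but it means two programmers following the SAP could print 0 or 14.5 for the same data. The CV definition sits in the section on NCA parameters, so its use in Table 35 is an inference.

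The consequence is small, and this stands in full. No hypothesis is tested, the NCA parameters do not use the concentration GM, and individual values appear in Table 35, Listing 31 and Figures 60 to 63. A zero GM would be visible to a careful reader. The largest bar effects come from an assumed CV of 100%; at 30% the offset is 4%.

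**Conclusion.** Both parts hold and should be fixed before reporting.

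The safeguard is wrong as written. A single zero-imputed value gives a GM of 0 by definition, and an undefined CV% if the log-scale definition applies to Table 35. Whether this occurred in the data is unknown; the 23% to 40% figures rest on assumed, independent BQL chances and six subjects.

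The mismatch between curve, bars and titles in Figures 64 and 66 is certain from the text. Its size, 4% to 41% in bar position, rests on log-normality and assumed CVs.

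The effect is confined to Table 35 and Figures 64 to 67. The late-BQL bias is minor, depends on late BQL values occurring, and is not needed for this conclusion.

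**What to change.** In SAP Section 8, keep the existing safeguard and extend it, for example: GM and CV% will be treated as missing for any set containing a value imputed as 0, or more than 1 BQL value, counted before BQL values are set to missing. Repeat the rule in the Table 35 footnote. The counting clause settles a point the text leaves open.

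Add a median row to Table 35. Section 5.1 lists the median among the summaries for continuous data, and the shell omits it.

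For Figures 64 and 66, choose either GM with GM ×/÷ geometric-SD bars or arithmetic mean ± SD, and make the Section 8 text and titles agree. Align the text and titles of Figures 65 and 67 in the same way.

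As a minor addition, print the number of BQL values at each time point, and flag or withhold the arithmetic mean where more than one value is BQL. No particular imputation method is required.

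The cost is SAP wording, one table row and minor programming. No new data are needed.
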